*Lignosus rhinocerus* TM02® as an immunomodulatory agent for the treatment of uncontrolled asthma: A prospective, open-label, single-arm, Phase II study.

#### **Time Frame of study:**

Expected start date : 01/07/2022 Expected end date : 31/05/2023

#### **Research Background**

#### Introduction

*Lignosus rhinocerus*, the Tiger Milk Mushroom, belongs to the *Polyporaceae* family and is one of the most important medicinal mushrooms used by natives in Southeast Asia and one of the most popular medicinal mushrooms used by indigenous communities of Peninsular Malaysia. It is known locally as "cendawan susu rimau" literally "mushroom of tiger's milk." It has traditionally been used by the Malays, Chinese and indigenous communities in Malaysia to treat a variety of diseases, including cough, asthma, fever, chronic hepatitis, gastric ulcer, liver and breast cancer and as a general tonic. In 2002, our former prime minister, Tun [name], mentioned that his chronic cough had been cured by this medicinal mushroom during his opening speech at BioMalaysia.

Since the inception of scientific research in 2002 into *Lignosus rhinocerus* TM02® (Tiger Milk mushroom) and its associated bioactivities by the Medicinal Mushroom Research Group (MMRG), [Faculty of Medicine, University of Malaya], they have revealed various relevant, solid scientific data that supports the translation of *L. rhinocerus* research into practical use. They have proven it to be safe for consumption (Lee et al, 2011, 2013). They have also identified the extract and fraction from *Lignosus rhinocerus* TM02® that play numerous roles in immunomodulation (Yap et al , 2020), anti-inflammatory (Lee et al, 2014), bronchodilating (Lee et al, 2018), anti-proliferative (Yap et al, 2013, 2017), antioxidative (Yap et al, 2013) and antiglycation (Yap et al , 2018).

MMRG has also subjected *Lignosus rhinocerus* TM02® to corticosteroid screening by Toxicology Laboratory, National Poison Centre. The results confirmed the absence of corticosteroid (Dexamethasone, Betamethasone, Costisone, Hydrocortisone, Prednisone, Prednisolone, Methyl prednisolone, Triamcinolone) as part of its ingredient.

*Lignosus rhinocerus* TM02® is marketed as "Tigerus Tiger Milk Mushroom Sclerotia" with a registration number of MAL 13025025TC. (Please see supporting documents for NPRA documents).

#### **Rationale of Study**

#### Asthma and FeNO

Asthma is a disease with marked heterogeneity in its clinical course and in its response to treatment. Variability in the type of airway inflammation may underlie this heterogeneity. Despite treatment with inhaled glucocorticoids, many patients continue to have uncontrolled asthma that requires more intensive therapy. Based on the ethnobotanical uses of Tiger Milk mushroom in treating asthma, its significant anti-inflammatory activity and also the positive feedbacks received from asthmatic volunteers using LiGNO™ Tiger Milk Mushroom, it is worthwhile to explore the potential of Tiger Milk Mushroom to be used as an immunomodulatory treatment to support conventional therapy through a proper designed clinical study. This will allow patients with uncontrolled asthma to obtain access to a new complementary therapy which they may benefit from. The objective of the study is to investigate the efficacy of L. rhinocerus to be used as a complementary therapy in improving symptoms, preventing exacerbations and reducing underlying airway inflammation in asthma patients.

 $FE_{NO}$  (fractional exhaled nitric oxide) is the only available point of care test to assess type-2 inflammation in asthma. Raised  $FE_{NO}$  with blood eosinophilia should be regarded as treatable traits of type 2 inflammation.  $FE_{NO}$  maybe useful for providing

feedback to both physicians and patients taking asthma therapy (in particular inhaled corticosteroids, ICS) particularly when the spirometry is normal.

 $FE_{NO}$  values can be influenced by several non-disease-related factors, thus filling in a questionnaire for NO measurement is recommended. Confounding factors could be related to the patient, like genetics, sex, weight and height, diet (*i.e.*, coffee) or taking drugs such as anti-inflammatory medications; also current smoking and atopy seem to influence  $FE_{NO}$  levels. Allergen exposure is associated with higher levels of  $FE_{NO}$  but they could decrease during the early phase of allergic response. Smoking is an important determinant of  $FE_{NO}$  levels and current smokers exhibit lower levels of  $FE_{NO}$  in comparison to ex-smokers and never smokers. Both active and passive smoking have effects on lowering  $FE_{NO}$  as demonstrated in healthy adults and in both adults and children suffering from asthma, regardless their allergy status.

 $FE_{NO}$  could be influenced also by viral respiratory infections. Age seems to be important too, especially in children, but correlation between age and sex has still to be defined. Recently, also ethnicity seems to have a role in  $FE_{NO}$  results, impacting clinical management.

Moreover, there are also technical confounding factors in  $FE_{NO}$  measurement, like the NO analyzer used, measurement technique, exhalation flow rate or nasal NO contamination. Spirometry could also influence  $FE_{NO}$  results, thus it should not be performed first.  $FE_{NO}$  could increase due to bronchodilation and it could decrease due to bronchoconstriction.

Reference values have been described for  $FE_{NO}$ . In clinical practice,  $FE_{NO}$  <25 ppb in adults is considered the normal value.  $FE_{NO}$  levels between 25-50 ppb in adults (20-35 ppb in children) should be contextualized within the clinical context.

The eosinophilic asthma phenotype is characterized by sputum eosinophils  $\geq$ 3% and identifies patients with a good response to corticosteroids and T2 immunomodulators. FENO values >50 ppb are likely connected with airway eosinophilic inflammation and this data may be used to predict a response to anti-inflammatory therapy, while low FENO <25 ppb correlates with less eosinophilic inflammation and responsiveness to corticosteroids. Diagnostic FENO cut point in well controlled asthma is usually indicated by normal values. FENO >30 ppb is usually associated with uncontrolled asthma.

According to GINA guidelines, following the diagnosis of severe asthma,  $FE_{NO} \ge 20$  ppb is considered the cut-off characterizing Type 2 inflammation severe asthma and it is used to assess this asthma phenotype, together with other markers like blood and sputum eosinophils. It has been suggested a  $FE_{NO}$  cut point of 21 ppb best fits  $\ge 3\%$  sputum eosinophils in corticosteroid-naive patients.

Very few data from studies analyzing clinically important change of  $FE_{NO}$  in individual patients is available and different are the results depending on the considered outcome. Considering simply the within-subject coefficient of variation, in healthy subject is approximately 10% (corresponding to a raw change up to 4 ppb) while it

increases to about 20% in patients with asthma, therefore leading the ATS experts to recommend a change of at least 20% to indicate a significant rise or fall in  $FE_{NO}$  over time or following an intervention.

The ATS makes the following recommendation:

- We recommend that low FENO less than 25 ppb be used to indicate that eosinophilic inflammation and responsiveness to corticosteroids are less likely.
- We recommend that FENO greater than 50 ppb be used to indicate that eosinophilic inflammation and, in symptomatic patients, responsiveness to corticosteroids are likely.
- We recommend that FENO values between 25 ppb and 50 ppb should be interpreted cautiously and with reference to the clinical context.
- We suggest using a reduction of at least 20% in FENO for values over 50 ppb or a reduction of more than 10 ppb for values lower than 50 ppb as the cut point to indicate a significant response to anti-inflammatory therapy.

We hypothesize that *Lignosus rhinocerus* TM02® can be used as a complementary supplement to support conventional therapy in asthmatic patients through a properly designed clinical study.

#### **Research Questions**

1. Can *Lignosus rhinocerus* TM02® reduce airway inflammation, improve symptoms and prevent exacerbations in asthma patients.

2. Can Lignosus rhinocerus TMO2® be used alongside conventional Western medications as per global guidelines to reduce airway inflammation, improve symptoms and prevent exacerbations in asthma patients.

#### **Problem Statement**

To date, there have not been any safe treatments that are void of side effects for the current respiratory related illnesses and/or pandemics. Based on the current handling procedures in health care centers, and as recently discussed in the Chinese Medicine Task Force Malaysia COVID19, it was revealed that natural products play an important role in alleviating and as adjunct therapy to present day Western medications. It is imperative that we thoroughly investigate the potential mode of action of these natural compounds, especially ones that has been proven safe for human consumption and with other known health benefits. In light of the current pandemic, *Lignosus rhinocerus* TM02®, which has been proven safe for consumption, contains synergictically acting biomolecules that will improve the quality of life of respiratory-related illnesses. This area of research is new, novel and has the potential to reveal valuable data for further pharmaceutical intervention studies.

## Objectives

The primary objective is to assess the effect of *Lignosus rhinocerus* TM02® in reducing airway inflammation by measurement of exhaled nitric oxide ( $FE_{NO}$ ) and to assess the effect of *Lignosus rhinocerus* TM02® in bronchodilation by measurement of trough forced exhaled volume in 1 second (FEV1).

The secondary objective is to assess the effect of *Lignosus rhinocerus* TM02® to be used as complementary therapy to improve symptoms and prevent exacerbations in asthma patients as assessed by the asthma control questionnaire (ACQ-7).

The tertiary objective is to assess the safety profile of *Lignosus rhinocerus* TM02® as complementary therapy in asthma patients.

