#### STUDY DESIGN AND SAMPLE SIZE

This is a prospective, open-label, Phase II study. The study will consist of a single treatment phase including:

- Screening period
- 12 weeks (90 days) of treatment period.

The planned sample size for this study is 17 subjects. In order to evaluate primary and secondary outcomes, study assessments will be conducted at Day 0, 30, 60 and 90 of treatment.

The MCID for FEV1 is 12% and 200 ml measured by spirometry obtained at baseline (immediately prior to the start of the treatment) with the results obtained 2 hour after administration of study medication (2-hour postdose FEV1) after 12 weeks of treatment.

The MCID for  $FE_{NO}$  is a reduction of at least 20% in  $FE_{NO}$  for values over 50 ppb or more than 10 ppb for values lower than 50 ppb will be used as the cut point to indicate a significant response to treatment.

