# Endpoints

#### **Primary Endpoints**

- Change in mean trough FEV1 expressed as mililitres after 90 days of treatment
- Change in mean ACQ-7 scores after 90 days of treatment
- The threshold for change in ACQ-7 scores that is considered clinically important (MCID) is 0.5.

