#### Secondary Endpoints

- Changes in mean FeNO (ppb) after 90 days of treatment
- Change in mean eosinophil count (cells/dL) after 90 days of treatment
- Changes in mean serum immunoglobulin E level (IU/ml) after 90 days of treatment

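### The aims and the FeNO cut point are worded as product effect, but one open-label arm yields only change from baseline, measured from what appear to be the qualifying screening values

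*Protocol*

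**What the plan says.** **Design.** The title calls the trial "A prospective, open-label, single-arm, Phase II study". The Study Design and Sample Size section repeats this: "This is a prospective, open-label, Phase II study. The study will consist of a single treatment phase". The protocol gives no concurrent control, historical reference value or performance goal.

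**Aims.** The Objectives section begins "The primary objective is to assess the effect of" the product, on airway inflammation (FeNO) and on bronchodilation (FEV1). The rationale, under Asthma and FeNO, says "The objective of the study is to investigate the efficacy of L. rhinocerus to be used as a complementary therapy". The Research Questions ask whether the product can lower inflammation, improve symptoms and prevent exacerbations. For FeNO, the design section adds that a fall of at least 20% (values over 50 ppb) or of more than 10 ppb (values below 50 ppb) "will be used as the cut point to indicate a significant response to treatment".

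**Endpoints.** The two primary endpoints are "Change in mean trough FEV 1 expressed as mililitres after 90 days of treatment" and "Change in mean ACQ-7 scores after 90 days of treatment". FeNO is listed among the secondary endpoints as "Changes in mean FeNO (ppb) after 90 days of treatment". All are within-patient changes.

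**Entry and baseline.** Inclusion requires uncontrolled asthma, FEV1 above 50% and below 80% predicted (up to three attempts at screening, and again before the first dose), and FeNO above 25 ppb at screening. The Day 0 visit list has no FeNO measurement and only a review of spirometry. The design section, by contrast, describes a baseline FEV1 taken immediately before treatment starts, and inclusion criterion (b) also calls for a pre-dose FEV1.

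**The concern.** The question asked is causal and the quantity measured is not. A mean change over 90 days in unblinded patients contains whatever the product does plus everything else that moves over the same period. The protocol itself supplies several such sources:

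- Its rationale lists diet, drugs, allergen exposure, viral infection and measurement technique as influences on FeNO.
- Patients stay on ICS/LABA while diaries, compliance checks and monthly visits are added, which could improve adherence to that background therapy.
- ACQ-7 is a questionnaire answered by patients who know what they are taking.
- Entry is restricted to patients whose readings lie on one side of a limit, so some return towards the usual level is to be expected.

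The last source is made worse if the reading that admitted the patient is also the baseline, which is how the Day 0 list reads for FeNO. At stake is what the trial may conclude. As worded, an FeNO fall past the cut point counts as a treatment response, and nothing in the design can contradict that reading.

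**Working it through.** The protocol states no alpha, power, SD or assumed effect with its sample size, so there is no planned figure to reproduce. The check asks how often the protocol's FeNO rule is met when the product does nothing.

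**Inputs from the protocol.** Within-subject CV of FeNO in asthma about 20% (about 10% in healthy subjects); entry at FeNO above 25 ppb; the two-part response rule; 17 subjects (the Study Population section says 10, a separate conflict).

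**Assumptions.** Lognormal FeNO, median 25 to 45 ppb before selection, between-patient log-SD 0.4 to 0.6, readings independent around a fixed patient level. CV varied over 10 to 30%.

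**By hand, for a patient well above 50 ppb.** The log-scale within-patient SD is s = √ln(1 + 0.20²) = √0.0392 = 0.198. The log ratio of two readings has SD 0.198 × √2 = 0.280. The chance of a fall of at least 20% with no true change is Φ(ln 0.8 / 0.280) = Φ(−0.797) ≈ 0.21. So about one such patient in five meets the rule by measurement variation alone.

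**By simulation, with selection above 25 ppb and no product effect.** Ranges are over the assumed medians and between-patient SDs.

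| CV | Meets rule, qualifying value as baseline | Expected of 17 | Spurious mean fall | Meets rule, separate Day 0 baseline | Mean change, Day 0 baseline |
|---|---|---|---|---|---|
| 10% | 2–4% | 0.4–0.7 | 0.1–0.5 ppb | 2–4% | about 0 |
| 20% | 17–20% | 3.0–3.3 | 0.4–1.8 ppb | 14–19% | about 0 |
| 30% | 29–32% | 5.0–5.4 | 1.1–3.6 ppb | 22–27% | about 0 |

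At CV 20% with the qualifying value as baseline, the probability of seeing at least 3 such patients of 17 is about 0.6 to 0.7.

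Two things follow. A separate Day 0 reading removes the spurious mean fall in FeNO. It lowers the proportion meeting the rule only modestly, because most of that proportion is measurement variation rather than selection. The label on the cut point therefore needs changing even if the baseline is corrected.

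**FEV1.** The protocol gives no within-subject variability for FEV1, so no figure is offered. Criterion (b) applies the 50 to 80% window to the pre-dose reading as well, so a Day 0 baseline would reduce selection bias for FEV1 but not fully remove it.

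**The case against.** The case on the other side has real content.

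- *Single-arm Phase II studies are legitimate.* They are, and the title says openly what this one is. The rationale also speaks of exploring potential, and the Problem Statement looks ahead to further intervention studies. That stands: the lack of a control arm is not the fault. But no section limits the conclusions to change from baseline, and the objectives ask for more.
- *The cut-point wording is borrowed.* It closely follows the ATS recommendation reproduced in the rationale, and it applies to FeNO only; the FEV1 and ACQ-7 thresholds are not worded this way. That also stands, so the relabelling concerns FeNO alone.
- *Expectation is the wrong threat for the quoted objective.* FeNO and FEV1 are measured quantities, and expectation bears mainly on ACQ-7. For the other two, the threats are selection, natural variation and adherence. ACQ score is not an entry criterion, so selection on it is at most indirect.
- *An SAP may handle this.* An SAP can choose a test. It cannot reword protocol objectives or supply a pre-dose reading that was never taken.

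A reader might infer three stronger things that the document does not support. One is that any improvement *will* be reported as efficacy; the protocol contains no reporting rule or success criterion for the mean change, so this is a prediction. Another is that the planned test has an inflated error rate. With an assumed two-sided 5% paired test, n = 17 and an inert product, an ACQ-7 drift of 0.25 would be significant 28% of the time at SD 0.7 (16% at SD 1.0), and a drift of 0.5, 79% (49%). But the protocol states no test, alpha or SD, so these figures are illustrative only. The third is that the screening-to-Day 0 interval could act as a control. Its length is not stated, and it precedes dosing, so it cannot capture 90-day drift or expectation on treatment.

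**Conclusion.** The point holds as a mismatch between what is claimed and what is measured, together with a baseline that appears to reuse the qualifying value. The causal wording is explicit in the rationale, Research Questions, Objectives and design section, and every endpoint is a within-arm change with no reference value.

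For size, at the protocol's own FeNO CV of about 20%, roughly 3 of 17 patients on an inert product would be labelled as responding to treatment. The spurious mean FeNO fall from reusing the screening value is small, about 0.4 to 1.8 ppb, but avoidable. These figures depend on the assumed FeNO distribution and, most of all, on the CV: the rate runs from 2–4% at CV 10% to 29–32% at CV 30%.

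That the screening values serve as baseline is an inference from the Day 0 list, and for FEV1 other sections say otherwise. The sections need reconciling in either case. The change is worth making before the trial runs, because it alters what can be concluded and a missing pre-dose reading cannot be recovered later.

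**What to change.** 1. **Wording.** In the rationale, Research Questions and Objectives, state the aim as estimating the change from baseline on add-on TM02. In the design section, replace the FeNO response label with *change exceeding the MCID*. Add a sentence that the results are hypothesis-generating and do not establish efficacy.
2. **Baseline.** Reconcile the Day 0 visit list with the design section and inclusion criterion (b). Schedule FeNO and then spirometry at Day 0, before the first dose; this order is already used at Day 90. Define those readings, not the screening ones, as baseline.
3. **Optional.** Show the screening-to-Day 0 change descriptively, with a note that it is not a control for the 90-day change.

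The cost is a protocol wording change, one FeNO and one spirometry reading at an existing visit, and a less favourable claim. No control arm is required for this fix. A causal conclusion would need a controlled trial.

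### FeNO and ACQ-7 exchange primary and secondary rank between the Objectives and the Endpoints, and the protocol does not say which list governs

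*Protocol*

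**What the plan says.** Protocol, Objectives: the primary objective has two measures. One is the effect "in reducing airway inflammation by measurement of exhaled nitric oxide"; the other is bronchodilation, assessed "by measurement of trough forced exhaled volume in 1 second". The secondary objective covers symptoms and exacerbations and is measured with ACQ-7.

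Protocol, Primary Endpoints: besides trough FEV1, the list has "Change in mean ACQ-7 scores after 90 days of treatment" and adds that "The threshold for change in ACQ-7 scores that is considered clinically important (MCID) is 0.5". Protocol, Secondary Endpoints: the first entry is "Changes in mean FeNO (ppb) after 90 days of treatment".

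Protocol, Study Design and Sample Size: this section mentions primary and secondary outcomes without naming them. It gives a threshold for FEV1, based on "results obtained 2 hour after administration of study medication", and one for FeNO that "will be used as the cut point to indicate a significant response to treatment". It also says that assessments take place at Days 0, 30, 60 and 90.

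Protocol, visit schedule: FeNO is listed at screening and at Days 30, 60 and 90. It is absent from the Day 0 list, even as a result to review.

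**The concern.** A protocol should fix its primary outcomes once. Here two current sections give incompatible answers for the second primary measure. The two candidates differ in kind: FeNO is a measured biomarker, while ACQ-7 includes patient-reported symptoms and is more exposed to expectation when subjects know what they take. They can disagree. If they do, the protocol offers text to support whichever one moved, and there is no control arm against which to check the result.

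Trough FEV1 is primary in both lists but is not a clean anchor, because the FEV1 threshold is defined on a 2-hour postdose value.

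The FeNO baseline is a separate matter, whatever rank FeNO has. If the only pre-treatment FeNO is the value that had to exceed 25 ppb for entry, regression to the mean will lower later values without any treatment effect.

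**Working it through.** **Rank conflict.** No arithmetic applies, so the sections are set side by side.

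| Measure | Objectives | Endpoints |
|---|---|---|
| Trough FEV1 | primary | primary |
| FeNO | primary | secondary |
| ACQ-7 | secondary | primary |

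Possible tie-breakers:

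- Study Design and Sample Size gives thresholds for FEV1 and FeNO, which matches the pairing in Objectives.
- The ACQ-7 threshold of 0.5 sits under Primary Endpoints, which points the other way.
- The Rationale and the Research Questions name symptoms and inflammation in opposite orders. Neither is a ranking.
- The sample size of 17 comes with no outcome, effect, variance or power, so it does not show which measure the trial was sized on.

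None of these is a governing statement.

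**FeNO baseline.** The protocol gives no figure to reproduce, so this is a sensitivity calculation with no drug effect.

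Inputs from the protocol:
- within-subject coefficient of variation of about 20% in asthma (Rationale);
- entry above 25 ppb (Inclusion Criteria, Screening);
- 17 subjects (Study Design and Sample Size).

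Assumptions, not in the protocol: true FeNO in the screened population is log-normal, with geometric mean (GM) 20 to 40 ppb and geometric SD (GSD) 1.4 to 2.0.

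Model: log FeNO = true value + independent error at each visit.
- Error variance: σ² = ln(1 + 0.20²) = ln 1.04 = 0.0392, so σ = 0.198.
- True-value SD: τ = ln(GSD). Total SD: s = √(τ² + σ²).
- Standardised cut-off: a = ln(25/GM)/s. Unselected mean: A = GM·exp(s²/2).
- Mean at screening among those selected: A·Φ(s − a)/Φ(−a).
- Mean at Day 90 in the same subjects: A·Φ(τ²/s − a)/Φ(−a).
- Spurious fall = the difference between these two means.

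Example, GM 20 and GSD 1.4: τ = 0.3365, s = 0.3904, a = 0.5715, A = 21.58. Screening mean = 21.58 × 0.4281/0.2838 = 32.56 ppb. Day 90 mean = 21.58 × 0.3891/0.2838 = 29.59 ppb. Fall = 2.97 ppb, or 9.1% of the screening mean. The simulated standard error of the mean change at n = 17 is 2.03 ppb, so the ratio is 1.46.

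All settings: fall in ppb, with its ratio to the standard error at n = 17 in brackets. The ratios come from simulating 3 million subjects per setting, and the simulated falls agree with the formula to within about 0.02 ppb.

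| GM (ppb) | GSD 1.4 | GSD 1.6 | GSD 2.0 |
|---|---|---|---|
| 20 | 2.97 (1.46) | 2.11 (0.86) | 1.38 (0.40) |
| 25 | 2.04 (0.89) | 1.56 (0.57) | 1.11 (0.29) |
| 30 | 1.38 (0.53) | 1.16 (0.38) | 0.90 (0.21) |
| 40 | 0.59 (0.18) | 0.64 (0.17) | 0.61 (0.12) |

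With an independent Day 0 repeat as baseline, Day 0 and Day 90 have the same expectation in the selected subjects, so the expected fall is 0. The simulation gave values within 0.04 ppb of 0 in all 12 settings. If the GSD is taken to include measurement error, the range becomes 0.5 to 3.6 ppb (0.12 to 1.96 standard errors).

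**The case against.** The rank swap itself is not in dispute. The case for giving it less weight is as follows.

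- **Only the second primary measure is affected.** Trough FEV1 is primary in both lists. This is right as far as it goes, but the mismatch between trough and 2-hour postdose FEV1 means that FEV1 cannot simply be relied on instead.
- **The Endpoints section is the natural place to look, and a SAP may fix the order.** Neither removes the problem. The protocol states no precedence, and a SAP could follow one list only by contradicting the other. It is fair to add that some front pages were not available for review, so the absence of a tie-breaker is established only for the text at hand.
- **No data are lost.** FeNO and ACQ-7 are both scheduled at Days 30, 60 and 90. This stands, but the risk lies in choosing the primary result afterwards.
- **The protocol may intend the screening FeNO as baseline.** The inclusion criterion calls it a baseline screening value, and Day 0 only reviews spirometry as well, although eligibility also calls for an FEV1 on the day of, and before, the first dose. This is a fair reading. It confirms that the selecting value would be the baseline, which is the source of the bias, and it shows that Day 0 needs attention for FEV1 too.
- **The FeNO bias may be small.** The Rationale links uncontrolled asthma with FeNO above 30 ppb. At assumed geometric means of 30 to 40 ppb the fall is 0.6 to 1.4 ppb (0.12 to 0.53 standard errors). Even 3 ppb is well below the 10 ppb response threshold. Study Population also gives 10 patients rather than 17; with 10 the largest ratio would be 1.46 × √(10/17) = 1.12. All of this stands and limits the weight of the baseline point. It does not touch the rank conflict.

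**Conclusion.** The contradiction is real and must be resolved. FeNO and ACQ-7 exchange ranks between two current sections, and nothing in the available text says which applies. This conclusion needs no number or assumption. It concerns the second of two primary measures, and it matters because the trial is open-label with no control group.

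The FeNO baseline gap is a lesser, separate point. The expected spurious fall is about 0.6 to 3.0 ppb, or 1 to 9% of the screening mean and 0.1 to 1.5 standard errors in 17 subjects. It rests on the assumed screening distribution and on the protocol's 20% within-subject variation. It is negligible if typical FeNO in those screened is near 40 ppb and material if it is near 20 ppb.

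**What to change.** - Before any outcome data are reviewed, adopt one ranking of trough FEV1, FeNO and ACQ-7 and use it identically in Objectives, Primary Endpoints and Secondary Endpoints. The documents do not show which ranking was intended, so the choice is the sponsor's. If outcome data have already been seen, say so and report the results under both rankings.
- Unless the SAP already does so, state whether success requires all primary measures or follows a fixed testing order.
- Reconcile trough FEV1 (Objectives, Primary Endpoints) with the 2-hour postdose FEV1 used for the threshold (Study Design and Sample Size) before any rule relies on FEV1.
- Reconcile Study Design and Sample Size with the Baseline visit so that FeNO is measured at Day 0 and used as baseline, with the screening value kept for eligibility. The first dose is taken the day after that visit, so the reading would precede treatment.

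The cost is wording in those sections and in the Baseline visit list, plus one FeNO measurement per subject at an existing visit (17 in all). One measure loses primary status, unless the sponsor chooses to keep both as primary and says how they are combined.

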## d) $FE_{NO}$ of > 25 ppb measured at baseline screening.

- Absence of a recent exacerbation 6 weeks prior to enrolment
- Non-smoker patient for at least six months and with a prior tobacco consumption < 10 packs/ year

- Patient with normal organ function
- Patient weight > 41 kg and body mass index (BMI) between 18 and 35 kg/m2

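### The protocol makes exacerbation prevention an objective judged by ACQ-7, but no endpoint records exacerbations and a single-arm trial cannot support a prevention claim

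*Protocol*

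**What the plan says.** Prevention of exacerbations appears as an aim in three places in the protocol:

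- **Rationale (Asthma and FeNO).** The study objective covers efficacy in "improving symptoms, preventing exacerbations and reducing underlying airway inflammation in asthma patients".
- **Research Questions.** Both questions ask whether the product can "reduce airway inflammation, improve symptoms and prevent exacerbations in asthma patients", the second of them alongside conventional medication.
- **Objectives.** The secondary objective is to "improve symptoms and prevent exacerbations in asthma patients as assessed by the asthma control questionnaire (ACQ-7"). This is the only place where an instrument is attached to the prevention aim.

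ACQ-7 appears once among the endpoints, as "Change in mean ACQ-7 scores after 90 days of treatment", with this rule for reading it: "The threshold for change in ACQ-7 scores that is considered clinically important (MCID) is 0.5". The other endpoints are the change in trough FEV1 (primary) and the changes in FeNO, eosinophil count and serum IgE (secondary).

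Outside the statements of aim, the protocol uses the term only to select subjects: "Absence of a recent exacerbation 6 weeks prior to enrolment".

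**The concern.** The protocol names a questionnaire score as the measure of an event outcome. A change in a mean control score describes how controlled the group is at a visit. It does not say how many subjects had an exacerbation, or how often. A reader who follows the Objectives section literally could take a fall in mean ACQ-7 as an answer to the prevention question.

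The absence of a comparator makes this worse. Prevention means fewer events than would otherwise have occurred, and nothing in this design shows what would otherwise have occurred. At stake is one of the trial's stated efficacy questions, repeated in three sections. The protocol itself fixes the objective, the instrument and the endpoint list, so the mismatch is not a detail left to a statistical analysis plan.

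**Working it through.** The protocol states no figure on exacerbations, so there is none to reproduce. The check is mainly a comparison of sections.

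**1. Endpoints against the aim.**

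| Endpoint | Level | Form | Observes exacerbations? |
|---|---|---|---|
| Trough FEV1 | Primary | Change in mean, 90 days | No |
| ACQ-7 | Primary | Change in mean score, 90 days | No |
| FeNO | Secondary | Change in mean, 90 days | No |
| Eosinophil count | Secondary | Change in mean, 90 days | No |
| Serum IgE | Secondary | Change in mean, 90 days | No |

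The result is 0 of 5.

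**2. Visit procedures against the aim.** No visit lists exacerbations as an item to collect. A daily symptom diary is issued at Baseline. Diary, adverse events and concomitant therapies are reviewed at Days 30, 60 and 90. Events may surface there, but the protocol gives no definition and links none of these sources to an outcome.

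**3. Comparator.** The title describes an open-label, single-arm study. No external or pre-treatment exacerbation rate is stated as a reference. The six weeks before enrolment cannot serve as one, because the inclusion criteria make them event-free by selection.

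**4. Who is in the Day 90 mean.** Under Early Withdrawal, subjects may leave for related adverse events or a need for prohibited medication, and are withdrawn if compliance falls below 75%. End-of-study evaluations are then done only if possible. A subject who has an exacerbation and leaves could therefore be missing from the Day 90 ACQ-7 mean.

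**5. Precision if events were counted.** The exact (Clopper-Pearson) two-sided 95% upper limit with 0 events in N subjects is 1 − 0.025^(1/N).

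- N = 17 (Study Design and Sample Size): 1 − 0.025^(1/17) = 0.195
- N = 10 (Study Population): 1 − 0.025^(1/10) = 0.308

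**6. Illustration with assumed rates.** The protocol gives no event rate, so 0.5, 1 and 2 exacerbations per patient-year are assumptions. Exposure is N × 90/365.25, which is 4.19 patient-years for 17 subjects and 2.46 for 10. Expected events are rate × exposure. Power is for showing a halved rate against a fixed, known rate, by a one-sided exact Poisson test at 0.025.

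| Assumed rate per year | N = 17: expected events | N = 17: power | N = 10: expected events | N = 10: power |
|---|---|---|---|---|
| 0.5 | 2.1 | 0% (no rejection region) | 1.2 | 0% (no rejection region) |
| 1 | 4.2 | 12% (reject only at 0 events) | 2.5 | 0% (no rejection region) |
| 2 | 8.4 | 21% (reject at 2 or fewer) | 4.9 | 8.5% (reject only at 0 events) |

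Even with a known reference rate, which the protocol does not supply, power would be low over this range.

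**The case against.** **The trial does look for trouble between visits.** The questionnaire is given at Days 0, 30, 60 and 90, and the Study Design section says that these visits serve the primary and secondary outcomes. Symptoms are recorded daily, and adverse events and concomitant therapies are reviewed repeatedly. This stands in part. A reader might infer that an exacerbation resolved before Day 90 leaves no trace in the data, and the documents do not support that. At most it holds for the Day 90 mean, and the protocol does not describe the questionnaire's items or recall period. The objection does not supply an exacerbation outcome, because none of these sources is turned into one.

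**Nothing obliges anyone to claim prevention.** The endpoint text speaks only of the mean score and its threshold of 0.5, and no decision rule links it to prevention. This also stands: a future misreport is a risk, not a stated plan. The Objectives section nevertheless names ACQ-7 as the measure of that aim, and this is the text to correct.

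**The numbers do not prove impossibility.** A reader might infer from the 19.5% limit that no version of this design could show prevention. That does not follow, because an upper limit means nothing without a background risk. At an assumed 1 event per patient-year, the 90-day risk is 1 − exp(−0.2464) = 21.8%, which is above 19.5%. The chance of no events in 17 subjects would be exp(−4.19), about 0.015. Zero events would then be a notable result against that rate, if the rate were known to apply. The limits illustrate imprecision only.

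**Few events?** A reader might also infer from the six-week exacerbation-free criterion that few events will occur whatever the product does. The documents give no rate, and subjects must have asthma uncontrolled on combination therapy with FEV1 between 50% and 80% predicted, which points the other way. The point does not need this premise.

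**Conclusion.** The point holds as a mismatch between a stated objective and its measure. Prevention of exacerbations is an aim in three sections, its only named instrument is a mean score, and none of the five endpoints observes it. A fall in mean ACQ-7 is not evidence of prevention.

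The conclusion that the trial cannot support a prevention claim rests on two facts in the protocol: no exacerbation endpoint, and a single arm without a reference rate. It does not rest on the confidence limits or on the assumed rates, which only show that a descriptive count in 10 to 17 subjects would be imprecise.

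The importance is moderate. The FEV1 endpoint, the planned sample size and the use of ACQ-7 for symptom control are unaffected. The mismatch should be corrected because it bears on what the trial may conclude and the correction is cheap.

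**What to change.** 1. Remove exacerbation prevention from the study objective in the rationale (Asthma and FeNO), from both Research Questions and from the secondary objective. All three sections need the edit, or the protocol will still contradict itself.
2. Limit the ACQ-7 objective to symptom control, and state that the trial will make no claim about preventing exacerbations.
3. If exacerbations are still of interest, add a definition to the protocol, fixed before data are reviewed, and one descriptive endpoint: the number and percentage of treated subjects with at least one exacerbation from Day 1 to Day 90, with an exact 95% confidence interval. Take events from the adverse-event, diary and concomitant-therapy reviews already scheduled. Keep all treated subjects in the denominator, count events that occur before early withdrawal, and show how many subjects left early without an event.
4. Two related items need reconciling in the same edit. The sample size is 17 in Study Design and Sample Size but 10 in Study Population. ACQ-7 serves the secondary objective but is listed as a primary endpoint.

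The cost is a narrower stated claim and, if step 3 is taken, one definition and one extra table. No new visit is needed. Without the definition, the count would be decided after the fact from a symptom diary and unstructured reviews, so step 3 should not be done without it.
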